3.1.6. Description of the population

- Participants to include in the ITT/PP analysis (n, %) – the denominator of the proportion is the number of participants enrolled
- Participants to exclude from the ITT/PP analysis (n, %) – the denominator of the proportion is the number of participants enrolled
- Reasons for exclusion from the ITT/PP analysis (n, %) – the denominator of the proportion is the number of exclusions from the analysis

3.2. DESCRIPTION OF DEVIATIONS TO THE PROTOCOL

3.2.1. Eligibility criteria assessment

- Participants with unmet eligibility criteria (n, %) – the denominator of the proportion is the number of participants enrolled
- Unmet eligibility criterion per participant

Verification of eligibility criteria is performed by the treating physician and nurses of participating centres prior to participant enrolment using data collected in the medical file. All eligibility criteria (inclusion and exclusion) are listed in Table 1 below.

Table 1. Eligibility criteria assessed by the treating physician and nurses prior to participant enrolment

Inclusion criteria	Exclusion criteria

1. ≥18 years of age2. Previously cured or spontaneously cleared HCV infection (i.e., positive HCV RNA test and/or positive anti-HCV antibody in the past with currently negative HCV RNA)3. Self-reported MSM4. Attending care at an human immunodeficiency virus (HIV) treatment centre (for participants with HIV) or a Centre for Sexual Health (CSH) or Centres gratuits d'information, de dépistage et de diagnostic (CeGIDD) (for participants without HIV)5. Sufficient understanding of Dutch or English (for participants in the Netherlands) or French (for participants in France)6. Accept to be contacted by telephone	
1. Acute or chronic HCV infection2. Participation in another study offering an HCV testing and/or an intervention targeting behaviours associated with risk of acquiring3. Receiving HCV treatment4. Being under legal guardianship (for participants in France)5. Not able or incapable to provide informed consent6. Suspected non-compliance with study procedures

7. Have health coverage within the national healthcare system (for participants in France)
 
8. Have access to internet and an e-mail messaging service
	
7. Individuals who are investigators or otherwise dependent persons are also not included in the study

---	---

3.3. PARTICIPANT CHARACTERISTICS

The following characteristics are described:

- Epidemiological characteristics at enrolment (M0)
- Clinical characteristics at enrolment (M0) and during follow-up (M6 to M24)
- Behavioural characteristics at enrolment (M0) and during follow-up (M6 to M24)

3.3.1. Epidemiological characteristics at enrolment (M0)

- Socio-demographic characteristics
 - Age (in years and in age groups)
 - Gender identity
 - Ethnicity
 - Educational level

3.3.2. Clinical characteristics at enrolment (M0) and during follow-up (M6 to M24)

- HCV-related clinical characteristics
 - Previous HCV infections (in counts)
 - Previous HCV treatment (yes/no)
 - HCV genotype
 - Time since first anti-HCV positive test (in years)
- HIV or pre-exposure prophylaxis (PrEP)-related clinical characteristics
 - HIV-status (positive or negative)
 - PrEP-use (yes/no)
 - Type of PrEP regimen (daily or event-driven)
- STI testing and testing outcomes (positive or negative), including chlamydia, gonorrhoea, genital herpes and/or syphilis (self-reported)

3.3.3. Behavioural characteristics at enrolment (M0) and during follow-up (M6 to M24)

- Sexual relationships and sexual behaviour
- Alcohol and drug use
- Influence of COVID-19 measures on sexual behaviour
- Influence of mpox on sexual behaviour

3.3.4. Intervention-related endpoints during follow-up (M12 to M24)

- Testing intervention-related endpoints
 - Including number of free HCV tests used (n, %) – the denominator of the proportion is the number HCV tests distributed.
 - Number of HCV positive test results (n, %) – the denominator of the proportion is the number of HCV tests distributed.
- Behavioural intervention-related endpoints, including website statistics (e.g. frequency of use, time spent on the intervention and the proportion of participants completing all modules of the intervention)
- Type of goals set in the behavioural intervention
- Usability and acceptability of testing and behavioural interventions

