4.4 Sample size calculation

We aim to have a minimum of 78 MSM per arm (total: 234). Assuming a drop-out rate of a maximum 5% in the run-in period (based on our experience with ongoing studies), we aim to enrol 246 MSM in total (see [Figure 1](#)). As we have no initial data on the effects of our interventions, we simulated power under varying conditions of at risk behaviour during the run-in period and absolute risk reduction during the intervention. With a sample size of 78 in each arm, we would have 80% power to demonstrate a statistically significant difference, at a type 1 error of 0.05, of a >22% reduction in the primary end-point from a 60% baseline prevalence of MSM identified as at risk (HCV-MOSAIC score ≥ 2.0 , see [Chapter 9.1](#)). When

testing for differences in reduction of the primary end-point between two intervention arms (**Chapter 9.1**), while additionally assuming a 10% reduction in the comparator arm, we would have 80% power to demonstrate a statistically significant difference if a reduction of 0.43 was observed in the other intervention arm.

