5.2 Arm II: home-based testing intervention

The second arm will consist of an additional patient-initiated home-based HCV testing service. The service will offer 4 free-of-charge HCV RNA tests, which can be obtained via email. It involves home-based HCV testing using self-sampled dried blood spots (DBS) (i.e., home-collection testing involving a certified laboratory) that was developed, used for purchase, and evaluated via the NoMoreC project (www.nomorec.nl) as part of the MC free initiative, a collaboration of relevant stakeholders that aims to reduce the incidence of HCV infections among MSM in Amsterdam. This service allowed men at high risk for HCV infection to take control and test for the presence of HCV-RNA. The self-sampling DBS has been previously validated and shown to be effective (see **Chapter 6**).

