7.1.3 Other study parameters

1. Characteristics of the study population:
 - a. Age
 - b. Ethnicity
 - c. Gender identity
 - d. Educational level
 - e. HIV-status
 - f. PrEP use
 - g. HCV history (number of infection(s), type of treatment, year of infection(s), impact of treatment(s))
2. Intervention-related endpoints: behavioural intervention
 - a. The proportion of individuals reporting change in the risk behaviour identified in the goal setting module of the behavioural intervention.
 - b. Website statistics: e.g., frequency of use, time spent on the intervention and the proportion of individuals completing all modules of the intervention.
 - c. Type of goals set in the behavioural intervention.
 - d. Usability and acceptability of the behavioural intervention.
3. Intervention-related endpoints: testing intervention

- a. The proportion of free HCV tests used (the total number of free HCV tests used divided by the total number of distributed tests).
- b. The proportion of HCV positive test results (the total number of HCV positive test results divided by the total number of free tests used).
- c. Usability and acceptability of the testing intervention.

4. The number of (home-based) tests obtained and used from other sources.

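### SAP 3.3.4 divides positive home tests by kits distributed, where protocol 7.1.3 divides by tests used; the SAP percentage is therefore positivity multiplied by uptake

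*SAP*

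**What the plan says.** Protocol 7.1.3 lists two proportions for the testing intervention among its other study parameters. Item 3a, uptake, is "the total number of free HCV tests used divided by the total number of distributed tests". Item 3b, the proportion of positive results, is "the total number of HCV positive test results divided by the total number of free tests used". Each has its own denominator.

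SAP 3.3.4 reports the same two quantities as a count with a percentage. For tests used it states that "the denominator of the proportion is the number HCV tests distributed", which agrees with item 3a. For positive results, on the next line, it states that "the denominator of the proportion is the number of HCV tests distributed", which does not agree with item 3b. I found no explanation of the change, and no other place in the SAP that gives the protocol's denominator. The SAP's own definitions section presents the document as a more detailed and technical account of the protocol's analysis.

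On how the kits reach men and get used, protocol 5.2 says "The second arm will consist of an additional patient-initiated home-based HCV testing service" and "The service will offer 4 free-of-charge HCV RNA tests". Arm III receives the same service (protocol 5.3).

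**The concern.** A kit that is never used cannot give a positive result. Including unused kits in the denominator turns a statement about the tests that were done into a mixture of two things: how often men tested, and how often a test was positive. Unused kits are to be expected here. Testing is at the participant's initiative, protocol 5.2 recommends it particularly when a man thinks he has been at risk, and the trial measures uptake as a parameter in its own right.

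At stake is the interpretation of one descriptive percentage. SAP 2.2.1 has descriptive results reported overall and by intervention group, so arm II and arm III will stand side by side. If the arms use their kits at different rates, the SAP percentages will differ even when the proportion of positive results among used tests is the same.

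**Working it through.** **Inputs from the documents**
- Four free tests per man in a testing arm (protocol 5.2).
- Two testing arms, II and III (protocol 5.2 and 5.3).
- A planned minimum of 78 men per arm (protocol 4.4).
- The two definitions of the positive-result proportion (protocol 7.1.3 item 3b; SAP 3.3.4).

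**Inputs assumed**
- Uptake of 25% to 100%, and 2% or 5% of used tests positive. The documents give no value for either, so there is no planned figure to reproduce.

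**Step 1: the identity.** Let P be positive results, U tests used and D tests distributed.

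- Protocol proportion = P/U
- SAP proportion = P/D = (P/U) × (U/D) = protocol proportion × uptake
- Relative shortfall = 1 − (P/D)/(P/U) = 1 − U/D = unused fraction

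This holds for any counts with U above zero. The two definitions agree only if every distributed kit is used, or if there are no positive results.

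**Step 2: illustration.** If every man in both arms receives all four kits, D = 2 × 78 × 4 = 624. With 2% of used tests positive:

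| Uptake U/D | Used U | Expected positives P | Protocol P/U | SAP P/D | Relative shortfall | Absolute shortfall |
|---|---|---|---|---|---|---|
| 100% | 624 | 12.48 | 2.0% | 2.0% | 0% | 0 points |
| 75% | 468 | 9.36 | 2.0% | 1.5% | 25% | 0.5 points |
| 50% | 312 | 6.24 | 2.0% | 1.0% | 50% | 1.0 points |
| 25% | 156 | 3.12 | 2.0% | 0.5% | 75% | 1.5 points |

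With 5% positive, the SAP figures at the same uptakes are 5.0%, 3.75%, 2.5% and 1.25%, and the absolute shortfalls are 0, 1.25, 2.5 and 3.75 points. The relative shortfalls are unchanged. The value of D cancels from every percentage, so the illustration does not depend on all 624 kits being sent out.

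**Step 3: comparison between the testing arms.** Suppose 2% of used tests are positive in both arms, with an assumed uptake of 60% in arm II and 30% in arm III. The SAP figures are 0.60 × 2% = 1.2% and 0.30 × 2% = 0.6%. The twofold difference comes wholly from uptake; under the protocol's definition both arms show 2.0%.

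**The case against.** The strongest reply is that little depends on this. The item is one of the protocol's other study parameters, and protocol 9.3 gives intervention-related outcomes descriptive analysis only. It enters no test, sample size or error rate. HCV reinfection is analysed separately, as a rate per person-year at risk (SAP 2.1.2 and 2.2.2), and this denominator does not touch it. SAP 3.3.4 reports both the number of tests used and the number positive, so the protocol's proportion is one division away. Positives per kit distributed is also a legitimate quantity, and the SAP states its denominator openly. All of this stands, and it keeps the point small. It does not explain why a pre-specified percentage departs from the protocol's definition without comment.

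A reader might infer more, and the documents do not support it:
- **That the planned modelling would be distorted.** Protocol 9.5 says that parameters will come from this study and from the literature, but does not name home-test positivity as one of them.
- **That the result could not be compared with other testing services.** The documents plan no such comparison, and the reported counts would allow it.
- **That the shortfall is large in absolute terms.** That depends on assumed values. The 5% case at 60% uptake gives 0.05 × 0.60 × 624 = 18.7 positives over 156 × 1.5 = 234 person-years, about 8 per 100 person-years. That is hard to square with the expectation in protocol 9.2 of few reinfections, so the 2% rows are the more cautious guide.
- **That the protocol defines a used test as one returned with a result.** It does not say how use is counted.

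**Conclusion.** The two documents define the same descriptive proportion with different denominators, and the SAP's version gives a different number whenever kits go unused and any test is positive. The SAP figure equals the protocol figure multiplied by uptake. The shortfall is relative, not a subtraction in percentage points: the SAP figure is three quarters of the protocol figure at 75% uptake, half at 50% and one quarter at 25%. The identity needs no assumption; the uptake and positivity values used to illustrate it are assumed.

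The SAP line nearly repeats the uptake line above it, which would fit a carried-over phrase, but the documents do not confirm that. It would go too far to read this as a bias in the trial's results: no primary or secondary endpoint is affected, and the protocol's proportion remains recoverable. It is a discrepancy worth correcting because the printed percentage, and any side-by-side reading of arms II and III, would otherwise mix uptake with positivity.

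**What to change.** In SAP 3.3.4, change the denominator for HCV positive results from tests distributed to free tests used, as in protocol 7.1.3 item 3b. Add a short statement of how a used test is counted, for example whether a returned sample without a valid result counts, and apply the same rule to the uptake numerator. Keep tests distributed as the denominator for uptake. If positives per kit distributed is also wanted, report it as a separately labelled measure.

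The cost is one changed phrase and one added sentence. The SAP already plans to report the counts of tests used and positive results, and no other analysis changes.

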3.4. PRIMARY ENDPOINT

3.4.1. Main analysis

- **Definition**

The proportion of participants achieving an HCV-MOSAIC risk score ≥ 2.0 compared between the run-in (i.e., M0 to M6) and intervention periods (i.e., M12 to M24). ORs are calculated along with their 95%CI in the ITT and PP population as described in paragraph 2.1.1.

3.5. SECONDARY ENDPOINTS

3.5.1. Incidence rate of HCV reinfections

- **Definition**

See paragraph 2.1.2.

Number of cases divided by the total person-years of follow-up at risk for HCV reinfection is calculated.

- **Handling of missing data**

Analysis is performed on all available data.

3.5.2. Incidence rate of STI (chlamydia, gonorrhoea, genital herpes and/or syphilis)

- **Definition**

See paragraph 2.1.2.

Number of chlamydia, gonorrhoea, genital herpes and/or syphilis infections divided by the total person-years of follow-up is calculated.

- **Handling of missing data**

Analysis is performed in available data.

3.5.3. Changes in HCV-related risk behaviour

- **Definition**

See paragraph 2.1.2.

Number of sex partners and condom less anal sex acts with casual partners are summarized using means with standard deviations or medians and interquartile range, depending on the distribution of the variable of interest. Counts and percentages for the individual risk behavioural items included in the HCV-MOSAIC risk score are also calculated. Differences in mean continuous outcomes with 95%CI are calculated using linear or Poisson regression coefficients (depending on distribution of outcome measure). Differences in odds of categorical outcomes (i.e., ORs) with 95% CI are calculated using logistic regression. A random-intercept for participant is added to each of the models described in this section.

3.5.4. Changes in sexual wellbeing

- **Definition**

Sexual wellbeing is assessed using three questions, which refer to pleasure and fulfilment from someone's sex life, using a 7-point Likert scale. Responses to these questions will be averaged, thereby summarizing into one continuous score.

Means and standard deviations or medians and interquartile range during run-in and interventions periods are described, depending on the distribution of the variable of

interest. Differences in mean continuous outcomes with 95%CI are calculated using linear or Poisson regression coefficients).

3.5.5. Differences in HCV-MOSAIC risk scores between arms

- **Definition**

The proportion of participants achieving an HCV-MOSAIC risk score ≥ 2.0 at the end of follow-up, compared between intervention arms.

ORs comparing arms and 95%CI are calculated.

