9. STATISTICAL ANALYSIS

9.1 Primary study parameter(s)

The primary outcome is the proportion at risk of HCV infection (as determined by a HCV-MOSAIC score ≥ 2.0) during the run-in versus intervention periods. The score is calculated by summing up the beta-coefficients specific to six self-reported risk factors when present in the previous 6 months (see [Chapter 7.1.1](#)). The HCV-MOSAIC risk score has been previously validated for acute (primary) HCV-infection in HIV-positive MSM and the optimal cut-off to predict HCV positivity was defined at ≥ 2.0 .(65) In addition, we recently evaluated whether the risk score could also identify individuals at high-risk of HCV reinfection, showing comparable performance (The Area Under the ROC Curve = 0.76) to that of primary acute HCV-infection.(66)

The six items of the HCV-MOSAIC risk score will be obtained using the answers from the study questionnaire every six months. The proportion achieving the primary outcome will be summarized at month 6, 12, 18 and 24 visits within each study arm. The probability of the primary outcome will be compared between the run-in (month 6) and intervention periods (month 12, month 18, month 24) using a mixed-effect logistic regression model. In this model, each individual will serve as their own control and between-individual differences at baseline will be accounted for using a random-intercept. Pre versus post-intervention odds ratios (ORs) and their 95% confidence intervals (CI) will be estimated and stratified on study arm, allowing us to identify interventions with significant differences. No multivariable adjustments will be applied. Additional analysis will be conducted in which ORs between arms will be compared by including and testing an interaction term between period and arm in the model (two arms at a time, for a possible three comparisons). No *p*-value adjustments will be made for multiple comparisons to avoid unnecessary correction on the possibly underpowered test for interaction.(67)

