1.4. SAMPLE SIZE

We aim to have a minimum of 78 individuals per arm (total of 234) who complete at least one study questionnaire during the intervention period. Assuming a maximum drop-out rate of 5% during the run-in period, 246 participants in total are needed to be enrolled. We simulated power under varying proportions at risk of HCV infection during the run-in period and absolute risk reduction during the intervention. With a sample size of 78 in each arm, we would have 80% power to demonstrate a statistically significant difference, at a type 1 error of 0.05, of a >22% reduction in the primary endpoint from a 60% proportion at risk of HCV infection during the run-in period.

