2.1.1. Primary endpoints

- **Definition**

The primary endpoint is the proportion at risk of HCV infection, as determined by the previously developed and validated HCV-MOSAIC risk score [1], which is compared between the run-in and intervention periods, within each arm.

- **Strategy for the main analysis**

Analyses are performed:

- By intent-to-treat (ITT): including all observations and analysed according to the intervention to which the participants were originally assigned, regardless of which intervention they received. This analysis assumes that any individual who was lost to follow-up did not achieve the primary endpoint (i.e., are at risk of HCV infection). Participants who are mistakenly included due to major eligibility criterion(a) not being met are removed from the analysis.
- By per protocol (PP): including all available observations and analysed according to the intervention to which the participants were originally assigned. This analysis excludes all observations after an individual has been lost to follow-up. Participants who are mistakenly included due to major eligibility criterion(a) not being met are removed from the analysis as well as participants who did not receive the intervention to which they were originally assigned.

- **Sensitivity analysis**

The following sensitivity analyses will be performed;

- Including only MSM who used the assigned intervention(s) (both ITT and PP).
- Including only MSM who were at risk of HCV infection at randomization, as determined by the HCV-MOSAIC score (both ITT and PP).
- Correction for issues in adherence and differential loss to follow-up (only PP): identifying pre-randomisation and post-randomisation covariates that predict adherence to the intervention. Depending on the mechanism of inadequate adherence and loss to follow-up, adjustment for confounding by adherence, g-methods or both will be entertained [2].

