2.1.2. Secondary endpoints

- **Definition**

Secondary endpoints are as follows:

- Incidence rate of HCV reinfections during both the run-in (i.e., M0 and M6) and intervention period (i.e., M12, M18, M24), both self-reported and laboratory-confirmed, defined as the number of cases divided by the total person-years of follow-up at risk for reinfection
- Incidence rate of any STI during the run-in and intervention period, both self-reported and laboratory-confirmed, defined as the number of chlamydia, gonorrhoea, genital herpes and/or syphilis infections divided by the total person-years of follow-up
- Other HCV-related risk behaviour during run-in versus intervention period, more specifically:
 - Changes in the mean or median number of sex partners (depending on the distribution of the variable of interest)
 - Changes in the mean or median number of condomless anal sex acts with casual partners (depending on the distribution of the variable of interest)
 - Changes in the proportion of participants reporting any individual behaviours that are included in the HCV-MOSAIC risk score
 - Changes in mean or median sexual wellbeing score (depending on the distribution of the variable of interest)
- The proportion of participants achieving an HCV-MOSAIC risk score ≥ 2.0 at the end of follow-up compared between intervention arms (in both ITT and PP populations)

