2.2.2. Comparative analysis

The primary endpoint is compared between the run-in period (i.e., at M0, M6) and at each time point during the intervention period (i.e., at M12, M18, M24) using a mixed-effect logistic regression model. In this model, each individual serves as their own control and between-individual differences at baseline are accounted for using a random-intercept. Odd ratios (OR) comparing the odds of run-in versus intervention time points, along with their 95% confidence intervals (CI), are estimated and stratified on study arm. These stratified analysis are performed by including an interaction term between arm and study time point (along with their individual covariate) in the model, while study time points are statistically tested within strata of the study arms. Comparisons between run-in and intervention time points are systematically conducted as follows:

- Unadjusted;
- Adjusted on the randomisation strata (country and, if sufficient numbers of individuals in each intervention arm are available, inclusion centre [3]);
- Adjusted on covariates that could potentially affect the evaluation of the primary outcome

Incidence rates of HCV reinfections and STIs are calculated during the run-in and interventions periods, separately. Considering that few HCV reinfections are likely to occur,

we intend to analyse the relative difference in incidence rates between periods using a Bayesian exponential survival regression model with non to weakly informative *a priori* distributions [4, 5]. The relative difference in incidence rates of STIs are compared between periods using a Poisson regression model with ln of person years of observation as an offset. These models are run on both the overall study population and stratified by treatment arm (using the same model configuration of fixed-effect covariates as in the primary endpoint).

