3.1.1. Flowchart

According to the CONSORT diagram [6]:

- Participants assessed for eligibility (n)
- Participants assessed for eligibility and not enrolled (n, %) – the denominator of the proportion is the number of participants assessed for eligibility
- Participants enrolled (n, %) – the denominator of the proportion is the number of participants assessed for eligibility
- Participants having completed the baseline study visit (n, %) – the denominator of the proportion is the number of participants enrolled
- Participants reaching M6 and were randomised (n, %) – the denominator of the proportion is the number of participants enrolled
- Participants having completed all study visits (n, %) – the denominator of the proportion is the number of participants randomized
- Withdrawals (n, %) – the denominator of the proportion is the number of participants enrolled

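### SAP 3.5.5 compares the randomised arms at the end of follow-up without using month 6 at-risk status; adjusting for it would be a cheap, optional and probably small gain in power

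*SAP*

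**What the plan says.** SAP 2.1.2 lists, as its last secondary endpoint, the proportion with an HCV-MOSAIC score of 2.0 or more "at the end of follow-up compared between intervention arms (in both ITT and PP populations"). SAP 3.5.5 repeats it as "The proportion of participants achieving an HCV-MOSAIC risk score ≥ 2.0 at the end of follow-up, compared between intervention arms" and adds only that ORs with 95% CIs are calculated. Neither section names a model, a covariate, a run-in term or the pairs of arms. Nor do they say that the end of follow-up means M24; SAP 2.3.1 ends follow-up at the last study visit.

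SAP 2.2.2 does not fill the gap. Its list of unadjusted and adjusted versions is introduced by "Comparisons between run-in and intervention time points are systematically conducted as follows". Its mixed model contains an arm-by-time term, but only to obtain results within each arm, "while study time points are statistically tested within strata of the study arms".

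Protocol 9.1 planned an additional analysis in which "ORs between arms will be compared by including and testing an interaction term between period and arm in the model", taking two arms at a time, and protocol 4.4 gave a power figure for it. The SAP neither carries this test forward nor says that it is dropped; SAP 1.4 keeps only the within-arm power.

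M6 status should be to hand. Participants are randomised at M6, and protocol 9.1 limits both the ITT and PP analyses to men who complete month 6 (the SAP does not restate that limit). M0 is less certain, because SAP 3.1.1 counts "Participants having completed the baseline study visit (n", %) separately from those reaching M6.

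**The concern.** When the same binary outcome is measured just before randomisation and again at the end, the earlier value is the natural covariate for comparing arms. It was fixed before allocation, so adjusting for it cannot distort the randomised contrast, and it removes the part of the outcome variance that it predicts. Leaving it out gives up some power at no saving.

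What is at stake is limited. This is a secondary contrast between active arms, so it gives no effect against standard care. Protocol section 3 describes the study as a pilot that looks for change within each arm.

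**Working it through.** **Inputs.** From the documents: 78 per arm, alpha 0.05 (taken as two-sided), 60% at risk in the run-in (protocol 4.4, SAP 1.4); assumed reductions of 10% and 0.43 in two arms (protocol 4.4). Assumed: 50% v 30% at risk at M24, and an M6-M24 within-person correlation ρ of 0 to 0.3. The documents give no correlation.

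**1. The plan's own figure.** For 60% v 38%, treating the two periods as independent:
- pooled-variance formula: Φ[(0.22√78 − 1.96√(2×0.49×0.51)) / √(0.24+0.2356)] = Φ[(1.943 − 1.386)/0.690] = 79.1%;
- unpooled formula: SE = √(0.4756/78) = 0.0781, and Φ(0.22/0.0781 − 1.96) = 80.4%.

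The stated 80% reproduces. It is a within-arm figure and says nothing about SAP 3.5.5.

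**2. SAP 3.5.5 as written, 50% v 30%.** SE of the risk difference = √[(0.25+0.21)/78] = 0.0768. Power = Φ(0.20/0.0768 − 1.96) = 74.0%.

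**3. Adjusted for M6.** The variance is multiplied by f = 1 − ρ².

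| ρ (M6-M24) | f | SE | Power | Difference from 50% detectable with 80% power |
|---|---|---|---|---|
| 0 | 1.00 | 0.0768 | 74.0% | 21.4 points |
| 0.1 | 0.99 | 0.0764 | 74.5% | 21.3 |
| 0.2 | 0.96 | 0.0752 | 75.7% | 21.0 |
| 0.3 | 0.91 | 0.0733 | 77.9% | 20.5 |

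**4. How large ρ can be.** For 60% at M6 and 30% at M24, the joint proportion is at most 0.30. So ρ ≤ (0.30 − 0.60×0.30)/√(0.24×0.21) = 0.12/0.2245 = 0.53. At ρ = 0.5 the joint proportion is 0.18 + 0.5×0.2245 = 0.292: about 97% of men at risk at M24 would have been at risk at M6, and only about 1.9% (0.0078/0.40) of those not at risk at M6 would be at risk at M24. The formula gives 85.3% power there, but that is almost at the limit. For 60% to 17% the ceiling is (0.17 − 0.102)/√(0.24×0.1411) = 0.37, so 0.5 is impossible.

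**5. The protocol's planning case.**
- Absolute reductions (50% v 17%), which fits the wording: SE = √[(0.25+0.1411)/78] = 0.0708, power 99.7% unadjusted. There is nothing useful to gain.
- Relative reductions (0.60×0.90 = 54% v 0.60×0.57 = 34.2%): 72.0% becomes 72.4 / 73.7 / 75.9% at ρ = 0.1 / 0.2 / 0.3.

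**6. Simulated logistic test, 50% v 28%** (near the unadjusted 80% point), 78 per arm, ρ being the M6-M24 correlation, 4,000 runs per setting:

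| ρ | Power, unadjusted | Power, M6-adjusted | Variance ratio, standardised risk difference |
|---|---|---|---|
| 0 | 81.9% | 81.6% | 1.00 |
| 0.2 | 81.3% | 82.5% | 0.97 |
| 0.3 | 81.5% | 85.2% | 0.91 |

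Adjusted type I error, simulated at 50% v 50%, was 4.9% to 5.6%. At ρ = 0.3 the mean log-OR SE rises from 0.340 to 0.363 while the OR moves from 0.38 to 0.34. The power gain comes from the larger conditional effect, not from a smaller SE on the OR scale.

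**7. What could shrink the gain.**
- Fading correlation (M0-M6 0.3 but M6-M24 only 0.17), 50% v 30%: simulated power 72.5% to 74.1%.
- The SAP's ITT rule, under which "any individual who was lost to follow-up did not achieve the primary endpoint (i.e., are at risk of HCV infection"), with an assumed 20% lost at random: 50.5% to 52.0%, and 50.5% to 53.6%, for M0-M6 correlations of 0.1 and 0.3.
- Fewer men at M24: the target of 78 counts those "who complete at least one study questionnaire during the intervention period", so it is an upper limit for M24. With an assumed 62 per arm, 64.1% becomes 64.6 / 65.9 / 68.2% at ρ = 0.1 / 0.2 / 0.3.

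**8. The protocol's interaction test.** For M6 against the mean of three later visits, with a constant effect and equal correlations, the variance factor relative to step 2 is (1+2ρ)/3 + 1 − 2ρ = (4/3)(1 − ρ). Power is 62 / 66 / 71 / 77% at ρ = 0 / 0.1 / 0.2 / 0.3. It is below the SAP's 74% until ρ reaches 0.25.

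**The case against.** The strongest reply is that nothing here is wrong. An unadjusted comparison of randomised arms is valid, the contrast is a secondary one in a pilot, and protocol 9.1 rules out multivariable adjustment. Most of this stands, and it is why the point is optional. The no-adjustment sentence, however, belongs to the protocol's run-in versus intervention analysis, where SAP 2.2.2 already adds adjusted versions. It is not a reason to leave a baseline value of the outcome out of the between-arm contrast.

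It is also fair to say that the gain is small at plausible correlations, and that on the SAP's chosen scale the standard error grows. Both are accepted.

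A reader might infer four stronger things that the documents do not support:
- That the between-arm result is biased. It is not; M6 status precedes randomisation.
- That the SAP does not say which between-arm test will be reported. It does: the end-of-follow-up OR, in ITT and PP. Only the fate of the protocol's additional test is unstated. The SAP describes its scope as the main analysis, so its silence is not a contradiction.
- That the SAP swapped a stronger test for a weaker one. Step 8 shows that the order depends on the unknown correlation.
- That power would rise to 85% or more. That needs a correlation close to its ceiling.

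**Conclusion.** The point holds as a cheap improvement to a secondary analysis, optional rather than essential. SAP 3.5.5 is valid but gives up the information in M6 status. For 78 per arm and 50% v 30%, the gain is from about 74% to about 75-78% power at an M6-M24 correlation of 0.1-0.3, with up to 9% less variance in the risk difference. There is none at zero correlation, and none of use if the protocol's 60% to 17% case is the true one.

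These sizes rest on an assumed correlation, assumed M24 proportions and the full 78 men per arm at M24. Losses counted as at risk, or a correlation that fades by M24, would make them smaller. The unresolved status of the period-by-arm test is a separate and minor matter of keeping the two documents in step.

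**What to change.** In SAP 3.5.5:
- name M24 as the time point;
- specify logistic regression of M24 at-risk status on arm and M6 at-risk status, for the three pairwise contrasts, in the ITT and PP populations;
- state how a missing M6 answer is handled;
- report a standardised (marginal) risk difference with 95% CI beside the OR, and say that the OR is conditional on M6 status.

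Separately, add one sentence saying whether the period-by-arm test in protocol 9.1 is kept as supportive or dropped.

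The cost is SAP wording only: no new data and no more participants. The downside is that the adjusted OR is conditional, lies further from 1 than the crude OR and has a larger log-scale SE. It must not be read as a crude OR, which is why the risk difference should stand beside it.
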